5.3. Number of Subjects

The planned total subject number is about 32 healthy volunteers for Part 1 in order to obtain 27 completed subjects. Subjects who have completed Part 1 will be rolled over to Part 2 to assess food effect on the PK profile of levamlodipine maleate tablets.

5.4. Treatment Assignment

Subjects receive the study treatments in Part 1 and Part 2 according to the following scheme

Part 1 (BE under fasted	Treatment A (Test Product)	A single dose of one 5 mg levamlodipine maleate tablet under fasted conditions (manufactured by CSPC Ouyi Pharmaceutical Co., Ltd., Hebei, China)					
conditions)	Treatment B (Reference Product)	A single oral dose of one 10 mg NORVASC [®] (amlodipine besylate) tablet under fasting conditions (manufactured by Pfizer Inc., New York, NY)					
	• Sequence 1	gned treatment sequences will be: (AB): Treatment A in Period 1; Treatment B in Period 2 (BA): Treatment B in Period 1; Treatment A in Period 2					
Part 2 (Food effect)	Test Product under fed conditionA single dose of one 5 mg levamlodipine maleate tab under fed conditions (manufactured by CSPC Ouyi Pharmaceutical Co., Ltd., Hebei, China)						
		Subjects should take a high-fat / high-calorie meal approximately 30 minutes prior to administration of the test product.					

5.5. Criteria for Study Termination

The Principal Investigator has the right to terminate the study in the interest of subject safety and welfare in consultation with CSPC Pharma. CSPC Pharma reserves the right to terminate or amend the study at any time for administrative reasons or if continuation of the protocol would present a potential safety risk to the subjects.

6. SELECTION AND WITHDRAWAL OF SUBJECTS

6.1. Subject Inclusion Criteria

To participate in the study, subjects must meet all the following eligibility criteria at screening or admission:

1. Are capable of giving informed consent and complying with study procedures;

- 2. Are between the ages of 18 and 45 years old, inclusive;
- 3. Women of childbearing potential (WOCBP) must have a negative pregnancy test at Screening and be practicing a medically acceptable method of contraception with an annual failure rate of less than 1% during the study and 60 days after discontinuation of study treatment. Women are considered not childbearing potential if they are > 1 year postmenopausal or surgically sterile (ie, hysterectomy, bilateral oophorectomy, or bilateral salpingectomy tubal ligation). If serum β HCG is the standard of care, then this value can be used to determine eligibility
- 4. Considered healthy by the Principal Investigator, based on a detailed medical history, full physical examination, clinical laboratory tests, 12-lead ECG and vital signs;
- 5. Nonsmoker, defined as not having smoked or used any form of tobacco in more than 6 months before screening;
- 6. Body mass index (BMI) of 19 to 30 kg/m² inclusive and body weight not less than 50 kg;
- 7. Willing and able to adhere to study restrictions and to be confined at the clinical research center.

6.2. Subject Exclusion Criteria

Subjects will be excluded from study entry if any of the following exclusion criteria are present at screening or admission:

- 1. Clinically significant history of gastrointestinal, cardiovascular, musculoskeletal, endocrine, hematologic, psychiatric, renal, hepatic, bronchopulmonary, neurologic, immunologic, lipid metabolism disorders, or drug hypersensitivity;
- 2. Subjects with a mean systolic blood pressure of three measurements >140 mmHg, or a mean diastolic blood pressure of three measurements >90 mmHg at screening. Blood pressure will be measured at sitting position.
- 3. Known or suspected malignancy;
- 4. Positive blood screen for human immunodeficiency virus (HIV), or hepatitis B surface antigen (HBsAg), or hepatitis C virus (HCV);
- 5. A history of seizure. However, a history of febrile seizure is allowed;
- 6. Positive pregnancy test result, or plan to become pregnant if female;
- 7. A hospital admission or major surgery within 30 days prior to screening;
- 8. Participation in any other investigational drug trial within 30 days prior to screening;
- 9. DSM-V substance use disorder within 6 months prior to screening;
- 10. A positive result for alcohol or drugs of abuse at screening or admission;
- 11. Tobacco use within 6 months prior to screening;
- 12. An unwillingness or inability to comply with food and beverage restrictions during study participation;
- 13. Donation or blood collection of more than 1 unit (approximate 450 mL) of blood (or blood products) or acute loss of blood during the 90 days prior to screening;
- 14. Use of prescription or over-the-counter (OTC) medications, and herbal medicines (including St John's Wort, herbal teas, garlic extracts) within 14 days prior to dosing;

- 15. A history of suicide attempt in the past 12 months and/or seen by the investigator as having a significant history of risk of suicide or homicide;
- 16. A history of intolerance or hypersensitivity to amlodipine or any excipients;
- 17. An unwillingness of male participants to use appropriate contraceptive measures if engaging in sex intercourse with a female partner of childbearing potential during the study and 60 days after discontinuation of study treatment. Sexual intercourse with pregnant or lactating women is prohibited.

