5. INVESTIGATIONAL PLAN

5.1. Study Design

This study consists of 2 parts. **Part 1** will be a randomized, open-label, single-dose, two-way crossover study to assess the relative BA of 5 mg of levamlodipine maleate tablets from CSPC (Test Product) versus 10 mg of Amlodipine Besylate Tablet NORVASC[®] from Pfizer Inc. (Reference Product) after a single oral administration under fasted conditions in male and female healthy subjects. Approximately 32 healthy volunteers will be enrolled for Part 1 to obtain 27 completed subjects.

Part 2 will be a single-arm, open-label, single-dose phase to assess food effect on the PK profile of levamlodipine maleate tablets from CSPC. Subjects who have completed Part 1 will be rolled over to Part 2 after a wash-out period for at least 14-days since the last dosing. Subjects will

receive a single oral administration of 5 mg levamlodipine maleate tablets from CSPC under a high-fat/high-calorie meal that should derive approximately 150, 250 and 500-600 calories from protein, carbohydrate and fat, respectively.

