7.1.2. Baseline (Day 0)

Subjects will be admitted to the CRU on Day 0 and remain sequestered at the CRU until the collection of the PK sample of 48 hours after dosing.

On arrival at the clinical research unit, all subjects will undergo the following assessments:

- Vital signs including blood pressure, heart rate, respiratory rate and temperature
- Three 12-lead ECGs will be recorded with 3-min interval at this visit. The means of the three ECGs will be used as the baselines.
- Overnight fasting blood sample collection for safety tests
- Drug/alcohol test
- Urine pregnancy test for females of childbearing potential
- Admission to the CRU for eligible subjects
- Assessment of AEs and concomitant medications

Enrolled patients will be fasted from 10 pm the day prior to dosing until approximately 4 hours after administration the next day (dosing day). Water intake will be permitted until 6 am of the dosing day.

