8. TREATMENT OF SUBJECTS

8.1. Methods of Assigning Subjects in Part 1

Subject treatment assignment will be based on a generated randomization scheme with a ratio of 1:1 (test: reference). Each treatment group will have 16 subjects randomized to receive either test drug or reference drug.

8.2 Methods of Assigning Subjects in Part 2

All subjects who have completed Part 1 will be rolled over to Part 2 after a wash-out period for at least 14 days since the last dosing to assess food effect on the PK profile of levamlodipine maleate tablets. Subjects will receive a single oral administration of study drug under a high-fat /

high-calorie meal. This meal should derive approximately 150, 250 and 500-600 calories from protein, carbohydrate and fat, respectively.

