2.3 Study Periods, Visit, and Day

The overall study consists of initial screening and three treatment periods, separated by two wash-out periods between treatment periods. Each treatment period includes a 3-day visit admitted in the CRU, followed by 5 daily visits. A reference date refers to the start date of the study drug administration for each treatment period. All efficacy and safety assessments at all visits will be assigned a day relative to this date within each treatment period. The relative day will be defined as: visit date – reference date + 1 for visits on or after the reference date, and visit date – reference date for visits before the reference date. Consequently there is no 'Day 0' defined.

In general, the baseline is defined as the last assessment before the intake of the first study medication during each treatment period unless specifically stated otherwise. All scheduled assessments after first administration of study drug will be used. Repeat/unscheduled assessments will not be used in descriptive statistics or any per-time point analysis, but will be shown in listings as applicable. Pre-dose unscheduled assessments will be taken into account for baseline determination and post first dose unscheduled assessments will be taken into account for worst-case determination as applicable.

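### Lactation is addressed for male subjects' partners but not for women who take the study drug, so the written criteria do not exclude a breast-feeding volunteer

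*Protocol*

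**What the plan says.** The trial enrols both sexes; Protocol 5.1 describes dosing "after a single oral administration under fasted conditions in male and female healthy subjects". Inclusion 2 sets the age range at 18 to 45.

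Two criteria deal with the reproductive status of female subjects:

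- Inclusion 3 (6.1): "Women of childbearing potential (WOCBP) must have a negative pregnancy test at Screening and be practicing a medically acceptable method of contraception". The contraception requirement runs through the study and for 60 days after treatment stops.
- Exclusion 6 (6.2): "Positive pregnancy test result, or plan to become pregnant if female".

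Lactation is named in one rule only, exclusion 17, which is about male participants. Its first sentence requires contraception with a partner of childbearing potential, again until 60 days after treatment stops. Its second sentence reads: "Sexual intercourse with pregnant or lactating women is prohibited". The Synopsis carries the same wording for all three criteria.

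**The concern.** Exclusion 17 puts pregnant and lactating women side by side as partners for whom male subjects must observe a restriction. For women who take the drug themselves, the criteria keep the pregnancy half of that pair and leave out the lactation half. As written, the rules go further for the partner of a dosed man than for a lactating woman who is dosed. The documents give no reason for the difference.

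What is at stake is participant protection. A site that follows the criteria exactly has no written ground to turn away a breast-feeding volunteer. If the drug reaches milk, which the documents do not discuss, her infant would be exposed in a healthy-volunteer study from which the infant gains nothing.

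**Working it through.** There is no planned figure to reproduce. The check is a reading of every place where lactation could be addressed, followed by a count of doses.

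**Where lactation could appear**

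| Place | What it covers for female subjects | Lactation named? |
|---|---|---|
| Inclusion 3 (6.1, Synopsis) | Negative pregnancy test, contraception | No |
| Inclusion 4 (6.1, Synopsis) | Investigator's judgement of health | No |
| Exclusion 6 (6.2, Synopsis) | Pregnancy or a plan for it | No |
| Exclusion 17 (6.2, Synopsis) | Conduct of male subjects only | Yes, as partners |
| Prohibitions (6.3) and withdrawal criteria (6.4) | Substances, medication, compliance, AEs | No |
| Screening (7.1.1) and medical history (11.1.1) | History, prior medication, demographics | No |
| Day 0 of Period One (7.1.2) | "Urine pregnancy test for females of childbearing potential" | No |
| Day 0 of Period Two and Part 2 (7.2.1, 7.3.1) | Urine pregnancy test | No |
| Laboratory assessments (11.1.5, Appendix A) | Pregnancy test | No |
| SAP 4.1 (discontinuation reasons) and 5.6 | Pregnancy; pregnancy screen listing | No |

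**Can a lactating woman satisfy what is written?** Inclusion 4 requires that she be "Considered healthy by the Principal Investigator, based on a detailed medical history, full physical examination, clinical laboratory tests, 12-lead ECG and vital signs". A breast-feeding woman can be healthy in that sense. Contraception is no bar in principle: 7.1.1 lists an intrauterine device among its examples. The age range does not keep her out.

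**Would a later step stop her?** Protocol 7.2 calls for an eligibility evaluation before Period Two, but the criteria available for it are the same ones. For the last dose, Protocol 8.2 says "All subjects who have completed Part 1 will be rolled over to Part 2".

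**Number and span of doses**

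- SAP 2.3: "The overall study consists of initial screening and three treatment periods". Part 1 gives 2 doses and Part 2 gives 1, so 2 + 1 = 3 for a completer.
- Each wash-out is at least 14 days from the previous dose (5.2, 7.3.1), so first to third dose takes at least 14 + 14 = 28 days.

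**How many women could be concerned?** Protocol 12.4 says only that an attempt will be made to enrol similar numbers of men and women. If that aim were met exactly, 32 / 2 = 16 subjects would be women. The documents give no basis for estimating how many of them might be lactating.

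**The case against.** Several stronger readings are tempting, and the documents do not support them.

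- *A reader might infer that criteria 6 and 17 contradict each other.* They do not. One governs the conduct of male subjects and the other governs entry of female subjects, and a site can obey both. Why exclusion 17 names lactating partners is not stated, so its purpose is itself an inference.
- *A reader might infer that infants would be exposed.* That requires transfer into milk. Neither the introduction, the adverse-event list nor the pharmacokinetic sections mention it.
- *A reader might infer that any breast-feeding woman passes every criterion.* Several provisions narrow the group. Exclusion 7 removes anyone admitted to hospital in the 30 days before screening. Exclusion 13 refers to acute blood loss in the 90 days before screening and may catch a recent delivery. Inclusion 4 leaves room for the investigator's judgement. Inclusion 7 requires willingness to be confined, and each period keeps the subject in the unit from Day 0 until the 48-hour sample, with daily visits to Day 8.
- *A reader might infer that half the sample is at issue.* Section 12.4 states a recruitment aim and not a quota, and only lactating women within that group are concerned.

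It can also be said that the consent form or investigator's brochure may deal with breast-feeding. Neither was available for this review, so that cannot be checked.

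What stands is that these points limit the size of the gap. None of them reaches a healthy woman many months after delivery who is willing to be confined, and consent wording would not take the place of an eligibility criterion.

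**Conclusion.** The concern holds as an unaddressed eligibility point. Under the written criteria, lactation is considered for the partner of a male subject and is not considered for a female subject.

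The conclusion rests on the protocol and SAP text alone. Being eligible here means not excluded by the written rules; an investigator could still decline to enrol her, but nothing requires it. The 28 days are the minimum dosing span and do not measure infant exposure. Few women are likely to be affected, though the documents give no figure for this.

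Nothing in the bioequivalence comparison, the food-effect comparison, the sample size or the safety analysis turns on the point. It merits correction because it concerns participant protection and is cheap to settle.

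**What to change.** 1. Reconcile exclusion 6 with exclusion 17 in both 6.2 and the Synopsis, so that lactation is addressed for female subjects as it is for male subjects' partners. Naming lactation in exclusion 6 is one way. If the sponsor means to admit lactating women, the protocol should say so and give the reason.
2. State the period that the lactation wording covers, in line with the 60-day post-treatment window already used in inclusion 3 and in the contraception sentence of exclusion 17. The sentence of exclusion 17 that names lactating women gives no period of its own, so the same edit can settle that.
3. Add a breast-feeding question to the screening medical history (7.1.1 and 11.1.1). Neither section lists one now, so the existing history cannot be relied on to find it.

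Cost: a phrase in two places and one screening question, with no new test. The downside is a very small number of extra screen failures. The planned 32 enrolled and 27 completed subjects need not change.

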6.3. Prior and Concomitant Medication and Substance

Illicit drug use and abuse of alcohol is prohibited prior to or during the study.

Subjects may not use tobacco containing products within 6 months prior to screening and at any time during the study.

The use of prescription medications or OTC products, including herbal product (e.g., St John's Wort, herbal teas, garlic extracts) is prohibited within 14 days prior to dosing.

After the subjects are enrolled and during the entire study period, subjects must adhere to the following prohibitions:

- Consumption of alcohol is not permitted within 48 hours prior to dosing and during the study
- Consumption of caffeine containing food or beverages is not permitted within 24 hours prior to dosing
- Use of acetaminophen at < 3g/day is permitted until 24 hours prior to dosing
- No administration of any prescription drugs, unless necessary for the treatment of an AE in the opinion of the Investigator.

All prescription medications and OTC products, including herbal products, taken in the 30 days prior to dosing or during the study period will be documented in the subject's source documentation and the case report form (CRF).

6.4. Subject Withdraw Criteria

Subjects will be informed that they have the right to withdraw from the study at any time for any reason without prejudice to their medical care. The Investigator also has the right to withdraw subjects from the study if it is in the best interest of the subject, or if the subject experiences an adverse event that warrants premature withdrawal.

Subjects may be withdrawn from the study if they:

- Have entered the study in violation of the protocol
- Use or require the use of prohibited concomitant medication(s)
- Are non-compliant with study procedures
- Experience an AE that warrants premature withdrawal

All treated subjects, should be followed according to the Schedule of Procedures. All subjects, even those who have discontinued prematurely, should have all evaluations for the End-of-Study visit performed, if possible. All procedures should be documented in the subject source documents and CRF. For all subjects who withdraw prematurely, the Investigator will indicate one of the following reasons for withdrawal on the CRF:

- Adverse event
- Death
- Protocol violation
- Lost to follow-up
- Subject's decision
- Other (reason to be specified by the Investigator)

In case of subjects' discontinuation from the study due to an AE, such subjects will be closely monitored until the resolution or stabilization of the AE. The Investigator should document the reason for discontinuation in the source documentation and CRF.

In the event that a subject withdraws participation from the study early, early withdrawal should be documented by the Investigator (or designee) in the appropriate CRF pages and source documents when confirmed.

7. STUDY PROCEDURES

The following sections describe in detail all study procedures. The schedule of procedures is presented in Table 5-1, Table 5-2, Table 5-3.

7.1. Part 1- Period One

7.1.1. Screening (Day -21 to -1)

Subjects will report to the CRU for a screening visit between Day -21 and Day -1 prior to the dosing. The following information and procedures will be performed and documented as part of the screening assessments:

- Prior to the performance of any study-related activities or evaluations, the subject must be thoroughly informed about all aspects of the study, including scheduled visits and activities. Each subject will sign the study-specific consent form prior to any screening procedures. A signed copy of the informed consent form (ICF) will be given to each consenting subject and another signed copy will be retained in the subject's study records.
- Medical history, including review of prior and ongoing medications taken in previous 30 days
- Physical examination including height and weight measurements. BMI will be calculated

- Vital sign measurements including blood pressure (three measurements), heart rate, respiratory rate and temperature. Subjects should be resting for at least 5 minutes prior to measurement. Vital signs will be measured in sitting position.
- A single 12-lead ECG (subject should be resting for at least 5 min prior to recording). ECG will be recorded in supine position
- Overnight fasting blood sample collection for safety tests as defined in Appendix A. HIV, and hepatitis B and C evaluations will be done at screening visit only
- Drug/alcohol test
- Serum pregnancy test at screening for females of childbearing potential.

Compliance with inclusion criteria and exclusion criteria will be verified against information collected and documented in the source documents and the CRF. Laboratory results obtained at screening will be used to verify eligibility.

Examples of contraception methods for participant or partner may include vasectomized partner (at least 6 months prior to dosing); intrauterine device; condom with spermicidal gel, foam, cream, film, or suppository; diaphragm with spermicidal gel, foam, cream, film, or suppository; or cervical cap with spermicidal gel, foam, cream, film, or suppository. A female of non-childbearing potential must have had at least 12 continuous months of natural (spontaneous) amenorrhea, follicle-stimulating hormone level > 40 mIU/mL at Screening, or have had surgical bilateral oophorectomy or hysterectomy > 6 weeks prior to Screening.

Once all inclusion criteria are met, exclusion criteria ruled out, and laboratory measurements obtained, eligible subjects will be scheduled for the admission (Day 0) visit within 21 days of screening.

7.1.2. Baseline (Day 0)

Subjects will be admitted to the CRU on Day 0 and remain sequestered at the CRU until the collection of the PK sample of 48 hours after dosing.

On arrival at the clinical research unit, all subjects will undergo the following assessments:

- Vital signs including blood pressure, heart rate, respiratory rate and temperature
- Three 12-lead ECGs will be recorded with 3-min interval at this visit. The means of the three ECGs will be used as the baselines.
- Overnight fasting blood sample collection for safety tests
- Drug/alcohol test
- Urine pregnancy test for females of childbearing potential
- Admission to the CRU for eligible subjects
- Assessment of AEs and concomitant medications

Enrolled patients will be fasted from 10 pm the day prior to dosing until approximately 4 hours after administration the next day (dosing day). Water intake will be permitted until 6 am of the dosing day.

